Throughout the BE-PEOPLE trial we will continue sampling all leprosy patients identified (Slit skin smears, blood sample, nasal and tongue swabs, tongue scraping, face mask sampling, a skin biopsy from the edge of non-facial lesions) on Anjouan and Moheli, with the aim of using molecular assays for *M. leprae* as quality assurance mechanism. If sufficient DNA is available Deeplex-MycLep will be used for typing the strains, which will allow us to perform highly sensitive surveillance for (traces of) resistance to rifampicin and bedaquiline. As part of BE-PEOPLE, we will moreover enroll all microbiologically confirmed tuberculosis patients on all islands of Comoros (Moheli, Anjouan, and Grande Comore, where bedaquiline will not be introduced, maximum 100 patients/ year) and assess whether they ever received (BE-)PEP or leprosy treatment. We will genotype their samples with Deeplex-MycTB XL, which includes all *M. tuberculosis* genes (potentially) involved in resistance to rifampicin and bedaquiline, to be able to detect the earliest traces of acquired resistance to these drugs, which is unexpected after single dose administration.

The overall goal of BE-PEOPLE is to validate a robust and safe leprosy PEP regimen, and its optimal administration, that prevents leprosy in the individual and interrupts transmission at the village level. If BE-PEP turns out to be safe and successful, we aim to adjust national guidelines in Comoros towards island wide implementation on Anjouan and Moheli, allowing to sustainably eliminate leprosy.

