2.2.2 Secondary

1. To assess effectiveness of the BE-PEP regimen at village level.

Outcome: The incidence rate ratio between villages that received BE-PEP and villages that received SDR-PEP.

2. To quantify frequency of potential adverse events such as gastro-intestinal (nausea, vomiting), nervous system-related (headache, dizziness) and cutaneous reactions.

Outcome: The proportion of participants treated with BE-PEP that report adverse events, with a breakdown by type of event.

3. To assess anti-PGL-I sero surveys as a tool to monitor leprosy transmission

Outcome: Age specific anti-PGL-I sero prevalence rates in villages belonging to arm 4 of the original PEOPLE trial at the time of the first survey round in 2019 and the final round of BE-PEOPLE in 2026

4. To monitor rifampicin and bedaquiline resistance among leprosy and tuberculosis patients

Outcome: We will quantify the prevalence of rifampicin and/or bedaquiline resistant strains of *M. leprae* and *M. tuberculosis* on each of the study islands making use of molecular markers.

5. To assess cost-effectiveness of the BE-PEP regimen compared to SDR-PEP.

Outcome: Cost per case averted between BE-PEP arm and SDR-PEP.

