1. Concurrent (within the last three week period before PEP administration) use of medication not present on the 'safe' list

Remarks regarding PEP distribution:

- Children between 2 and 5 years of age or weighing between 10 and 20 kg or people taking medication from the unsafe list will be excluded from BE-PEP and offered SDR-PEP if eligible.
- Study participants living in the PEP zone but ineligible for PEP due to the PEP inclusion or exclusion criteria or being absent during the village PEP distribution round will not be automatically included in the PEP distribution the following year. It is possible that a study participant is not eligible one year due to the PEP inclusion or exclusion criteria but will be eligible for PEP the next year when the household is again part of the newly calculated PEP zone and the individual inclusion or exclusion criteria are respected.
- Household contacts of an index case in the BE-PEP arm absent during the 1st annual PEP distribution but present during the 2nd annual PEP distribution will only be offered PEP once that year and will not be revisited after 30 days.
- Participants who are not BE-PEP eligible due to concomitant medication not present on the 'safe list' can be provided SDR-PEP, provided they do not meet any other exclusion criteria.
- Children who are not BE-PEP eligible solely for not meeting age and weight criteria, can be provided SDR-PEP if aged 2 years or above and weighing 10 kg or above.

All leprosy patients diagnosed during the study period, even those from non-study villages, will also be enrolled in a sub-study in which potentially a nasal/tongue swab, a tongue scraping sample, face mask sample and skin biopsies will be collected from non-facial lesions. qPCR on these samples will allow to verify the accuracy of the clinical diagnosis and further processing with Deeplex Myc-Lep V3 of qPCR positive samples (or WGS if needed), will allow to monitor drug resistance and assess the impact of the intervention on transmission of *M. leprae*. As drug resistance may also affect treatment for tuberculosis, we will also sample all GeneXpert positive tuberculosis patients identified on Anjouan, Mohéli, and Grande Comore during the study period for drug resistance testing with Deeplex Myc-TB XL, and verify whether they received rifampicin and/or bedaquiline in the past.

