7.3 Surveillance for selection for mycobacterial drug resistance

The risk of inducing rifampicin resistance in (undiagnosed) tuberculosis or leprosy patients with one single dose of the drug is negligible.[40] As was described by Mitcheson for treatment of tuberculosis, resistance emerges as a result of selection of resistant mutants under conditions of monotherapy.[41] This requires high numbers of bacilli as observed in cavitary pulmonary tuberculosis, combined with prolonged exposure, as mycobacteria are slow to replicate. Repeated cycles of starting a treatment regimen, interrupting treatment, and restarting after some days can mimic monotherapy because of differential activity of drugs during the first days of treatment. However a single dose of rifampicin, possibly repeated once after four weeks, will not result in drug resistance. The BE-PEP regimen consists of two drugs, rifampicin and bedaquiline, further reducing the risk of selection of resistant mutants, although the half-life of bedaquiline and its metabolites far exceeds that of rifampicin.

To further decrease any potential risk of acquired drug resistance we will screen for signs and symptoms of pulmonary tuberculosis and exclude those participants from PEP.

We will also monitor molecular resistance for rifampicin and bedaquiline on samples from all leprosy patients, using an expanded Deeplex MycLep assay in which the *atpE* gene of *M. leprae* is included and using whole genome sequencing. Lastly, we will also recruit presumptive tuberculosis patients in Comoros for analysis of sputum and/or tongue swabs and genotype extracted *M. tuberculosis* DNA with the Deeplex MycTB XL, which includes additional targets potentially associated with bedaquiline resistance. Whole genome sequencing may be used to track the spread of drug resistant TB.

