9.3.2 Secondary analyses

In a second analysis we will calculate the incidence rate ratio of leprosy at village level between arms 1 and 2. Here all participants enrolled will be taken into account, even those that did not receive PEP. A similar model as in the primary analysis will be used, including all persons in the villages randomized, even those who were not eligible to receive the study treatment due to age or weight restrictions.

Prespecified adverse events such as gastro-intestinal (nausea, vomiting), nervous system-related (headache, dizziness) and cutaneous reactions will be tabulated and presented using counts and percentages. Comparisons between study arms will be done using Fisher's exact test.

In the villages that were originally allocated to arm 4 of the PEOPLE trial, the fourth and final screening round will be accompanied by one final anti-PGL1 sero-survey. Based on the comparison of age specific anti-PGL-I sero-prevalence rates at the time of the 2019 survey and in the final survey in 2026, we will assess the potential of anti-PGL-I surveys as a tool to monitor leprosy transmission. We will compare seroprevalence rates in different age groups of 2019 to 2026, both overall and by village and island to assess whether a trend can be identified and whether this trend is consistent across villages/islands. This analysis will be primarily descriptive.

Cost data will be gathered throughout the study and used to calculate the average cost per person screened for leprosy by island, average cost per case detected by island. If BE-PEP is shown to be more effective than SDR-PEP, a cost-effectiveness analysis will be done estimating the average cost per case of leprosy averted by study arm and by island. Incremental costs will be calculated using the SDR-PEP arm (arm 2) as baseline.

Prevalence of bedaquiline and/or rifampicin resistant strains will be calculated per island with in the numerator all leprosy patients with rifampicin or bedaquiline resistant isolates identified and in the denominator all patients tested. Along with the proportions 95% confidence intervals using the Wilson's method will be calculated.

Results of genotyping of *M.leprae* will be analyzed separately in the framework of the project titled: 'Improving leprosy prevention strategies by integrating social network analysis with spatial and molecular epidemiology data of *Mycobacterium leprae* in the Comoros'.

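### The planned resistance analysis omits tuberculosis and is not split by PEP exposure, so resistance could be seen but not attributed to a regimen

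*Protocol*

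**What the plan says.** Section 2.2.2, secondary objective 4, is "To monitor rifampicin and bedaquiline resistance among leprosy and tuberculosis patients". Its outcome reads "We will quantify the prevalence of rifampicin and/or bedaquiline resistant strains" of both species, on each study island, from molecular markers.

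Section 9.3.2 turns this into one calculation: prevalence "calculated per island with in the numerator all leprosy patients with rifampicin or bedaquiline resistant isolates identified" and "in the denominator all patients tested". It adds "Along with the proportions 95% confidence intervals using the Wilson's method will be calculated". No other breakdown or comparison of resistance is given there.

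Exposure information is to be collected. For tuberculosis patients the Synopsis undertakes to "assess whether they ever received (BE-)PEP or leprosy treatment", and section 4.2 to "verify whether they received rifampicin and/or bedaquiline in the past". For trial participants, sections 6.2 and 11.1 place PEP dose and intake in the database. Sections 3.1 and 4.3 enrol Grande Comore tuberculosis patients as controls, because bedaquiline is not used there and low-level *Rv0678* variants occur without exposure.

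The SAP supplied covers phase 2 only and does not address resistance.

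**The concern.** Whether a regimen selects for resistance is a question about exposure: is resistance found more often after BE-PEP than after SDR-PEP or no PEP? Island is a poor stand-in for exposure, because sections 3.1 and 4.4 randomize clusters to both regimens within Anjouan and within Mohéli. Section 3.1 also samples leprosy patients from non-study villages, and section 4.2 puts the study population at about 30% of the two islands.

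The numerator also pools resistance to either drug. Rifampicin is given in both arms and bedaquiline in one, so the two carry different information.

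For tuberculosis, the objective, the control island and the exposure question are all in place, but section 9.3.2 defines no numerator. If resistance appeared, the trial would report a prevalence and a reader could not tell which exposure group it came from. Section 3.1 describes monitoring for the earliest signs of resistance as imperative, so this matters when the regimen is considered for wider use.

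**Working it through.** **1. Stated purpose against stated analysis**

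| Element | Elsewhere in the protocol | Section 9.3.2 |
|---|---|---|
| Species | *M. leprae* and *M. tuberculosis* (2.2.2) | Numerator: leprosy patients only |
| Denominator | – | All patients tested; species not stated |
| Drug | Rifampicin and bedaquiline | Either, pooled |
| PEP exposure | Recorded (Synopsis, 4.2, 6.2, 11.1) | Not used |
| Unexposed control | Grande Comore tuberculosis patients (3.1, 4.3) | Not used |
| Split | Arms randomized within island (3.1, 4.4) | Island |

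**2. Reproducing the protocol's figures.** qPCR yield in PEOPLE (3.1): 755/1,030 = 73.3%, as stated. Cluster size (4.3): 2,819 × 0.73 × 0.83 = 1,708. Total: 44 × 1,708 = 75,152, as stated.

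**3. Expected cases among PEP recipients over three years** (risks from 4.3: 0.0033 with SDR-PEP, halved to 0.00165 with BE-PEP)
- Recipients per arm: 22 × 1,708 = 37,576.
- BE-PEP: 37,576 × 0.00165 = 62 cases.
- SDR-PEP: 37,576 × 0.0033 = 124 cases.

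**4. How many would be genotyped.** The past yield is 260 extracts with enough DNA from 1,030 patients sampled, or 25.2%. That gives 62 × 0.252 ≈ 16 and 124 × 0.252 ≈ 31. This divides extracts by patients, and section 5.2.4 expects enough DNA from all MB patients and some PB patients, so the yield may be higher. Genotyping is limited to RLEP-positive extracts, so 73.3% is a ceiling if the qPCR yield holds: 62 × 0.733 ≈ 45 and 124 × 0.733 ≈ 91.

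**5. What an island figure mixes.** Take 62,000 people per arm and apply the same two risks to everyone in the arm (an assumption). Study clusters then yield 62,000 × 0.0033 + 62,000 × 0.00165 = 205 + 102 = 307 cases.
- BE-PEP recipients: 62/307 = 20%.
- SDR-PEP recipients of BE-PEP age and weight: 124/307 = 40%.
- Everyone else (undosed, or below the BE-PEP limits): 121/307 = 39%.

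If BE-PEP adds nothing, recipients are 124 of 124,000 × 0.0033 = 409, or 30%. Non-study villages lower these shares by an amount the documents do not give.

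**6. Illustration with two resistant isolates.** At 25.2%, 307 cases give about 78 genotyped. Split 34:10 by clusters (4.2), assuming equal cluster sizes, that is about 60 on Anjouan and 18 on Mohéli.

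| Figure | Proportion | Wilson 95% CI |
|---|---|---|
| Among BE-PEP recipients, both islands | 2/16 = 12.5% | 3.5–36.0% |
| Island figure, both cases on Mohéli | 2/18 = 11.1% | 3.1–32.8% |
| Island figure, both cases on Anjouan | 2/60 = 3.3% | 0.9–11.4% |

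Each island figure is the same whether the two patients had BE-PEP, SDR-PEP or nothing. The PEOPLE baseline is 0/260 (Wilson 0–1.5%), so either case would be noticed. What is missing is the exposure behind it.

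**7. What a split by exposure can deliver.** 2/16 against 0/31 gives Fisher p = 0.11; 3/16 against 0/31 gives p = 0.035. A clean 0/16 still has a Wilson upper limit of 19.4%. The table can describe, but not settle, a difference.

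**8. Tuberculosis.** At 50–60 patients a year (4.3), three to four years give 150–240, or 300–400 at the Synopsis cap of 100 a year. BE-PEP recipients are 37,576/(124,000/0.30) ≈ 9% of the two islands. If 30–70% of tuberculosis cases arise there (an assumption; no figure is given), three years give about 4 to 11 patients among recipients, or up to 19 at the cap.

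**The case against.** Several defences carry weight.

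- **Tuberculosis is a stated outcome.** Section 2.2.2 names *M. tuberculosis*, and the word leprosy in section 9.3.2 restricts only the numerator. This looks like a drafting gap rather than a decision to discard the data. That stands, and it is why the two sections need reconciling.
- **The objective is to monitor prevalence, not to compare regimens.** For leprosy, section 9.3.2 does match the objective's wording. But section 7.3 is framed around selection, and section 1.2 cites two patients who developed leprosy after rifampicin PEP, without resistance, as relevant evidence. The investigators already read resistance against exposure.
- **Other plans may cover it.** Section 9 defers to a binding SAP, and section 9.3.2 sends *M. leprae* genotyping to a separate project. Neither a phase 3 SAP nor that project's plan is among the documents, so they may contain more. Nothing shown describes a resistance analysis by exposure or one for tuberculosis.
- **The risk is thought small.** Section 7.3 calls the risk of inducing rifampicin resistance with one dose negligible. It says two drugs reduce selection further, "although the half-life of bedaquiline and its metabolites far exceeds that of rifampicin". The Synopsis calls acquired resistance unexpected. These are reasons for a modest table, not for none.

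A reader might infer that the pooled figure would hide resistance altogether. The documents do not support that. With 0/260 at baseline and no rifampicin-resistant tuberculosis yet observed (4.1), a single resistant isolate would stand out as a count. The percentage need not fall much either, as the Mohéli row shows. A reader might also infer that splitting by PEP history would prove or exclude selection by BE-PEP; the cell sizes rule that out.

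**Conclusion.** The point holds as a mismatch between objective and analysis, and as a loss of attribution. Section 9.3.2 does not deliver the tuberculosis half of objective 4, leaves the Grande Comore controls unused, and splits by a factor that mixes the exposure groups. Detection of a resistant strain is not lost.

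BE-PEP recipients would be about 20% of study-cluster leprosy cases, or 30% if BE-PEP adds no benefit, and less once non-study villages are counted. About 16 would be genotyped at the past yield, and at most about 45. These figures rest on the section 4.3 risks and coverage and on PEOPLE laboratory yields. The island split in the illustration also assumes equal cluster sizes.

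The primary efficacy result is unaffected. The change is worth making because it replaces a less informative split at little cost, not because it would give a powered comparison.

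**What to change.** In section 9.3.2, and in the phase 3 SAP:

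1. Reconcile with section 2.2.2 by reporting *M. leprae* and *M. tuberculosis* separately. Give each its own denominator (patients of that species with an interpretable resistance result), and report rifampicin and bedaquiline separately as well as combined.
2. Add one descriptive table of resistant over tested, by PEP received before diagnosis (none, SDR-PEP, BE-PEP) and, for study clusters, by randomized arm, with Wilson intervals. Show non-study villages separately, and state how rifampicin given in PEOPLE is classified.
3. Make Grande Comore tuberculosis patients the bedaquiline-unexposed control row.
4. State that the table is descriptive and that no formal conclusion between regimens will be drawn from it.

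Splitting BE-PEP into one and two doses, and sending the table to the DSMB, are optional.

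The cost is protocol and SAP wording, one table, and linkage of laboratory results to PEP records already held. The documents state an exposure check for tuberculosis patients and intake records for trial participants. For leprosy patients from non-study villages, exposure would be inferred from residence unless it is asked.

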9.3.3 Interim analyses

An interim analysis will be conducted upon completing the second door-to-door survey after randomization, in early 2025. This analysis will include both the individual effect of PEP and the effect of PEP at village level, as described above.

10. MONITORING AND QUALITY ASSURANCE

The clinical research scientist of CTU will perform on-site monitoring visits, with the purpose of source document verification and follow-up of local study implementation in line with ICH-GCP guidelines (including e.g. investigator file completeness). The monitoring activities and frequency will be described in a monitoring plan. A report detailing the actions taken during the monitoring visit will be written and shared amongst the study team.

The coordinating investigator will also visit the study team at regular intervals for project coordination and follow-up.

A pharmacist in Comoros has been trained on GCP and will serve as local quality responsible IP management such as completing inventory- and temperature log monitoring). The PI and involved site research staff will allocate adequate time and resources for such monitoring activities.

The sponsor will inform the Investigators concerned immediately upon notification of a pending study centers inspection by any regulatory authority or funder. Likewise, the investigator will inform the sponsor of any pending inspection.

11. DATA MANAGEMENT

In the BE-PEOPLE study for the baseline survey we will continue to use formats developed in the PEOPLE study consisting of a paper survey form, three forms in an Android app and an Access database with barcode, name, age and gender of each participant enrolled. After the baseline survey in 2022, which partly overlaps with the final survey of PEOPLE, we will shift from ODK Collect used in the PEOPLE trial to REDCap, which is GCP compliant. REDCap will also be used in the phase 2 study in 2022.

Data Management will be performed by the CTU data managers in collaboration with the Principal Investigator and with the study staff involved in collecting and handling the study data. The continued follow-up of the cohort of leprosy patients established during the PEOPLE trial and the preceding ComLep trial, of which drug resistance surveillance is a part, we also shift to REDCap. Drug resistance surveillance will be extended to tuberculosis patients, data collection for this part will also be integrated in the REDCap database.

A separate Data Management Plan will be prepared, with following essential aspects:

11.1 Data collection, handling and retention

The phase 2 study organized in 2022 will consider the collecting and managing of participant-level data comprising medical data and in particular safety data referring to adverse events, medical history, concomitant medication, ECG and liver function tests.

The phase 3 study starting in 2023 will finish after the fourth and final annual screening round. The phase 3 study will consider the collecting and managing of household-level data (Household ID, geographic coordinates) and participant-level data (participant ID, demographic, health and medical data with reference to examinations, leprosy and TB diagnosis and treatments, registration of PEP eligibility and intake, averse event monitoring).

Both studies will have their own database and be based on a system of data collection and management via electronic questionnaires on mobile devices (smartphones, tablets and/or laptops), by using REDCap.

REDCap (Research Electronic Data Capture) is a software widely used in the academic research community for building and managing surveys, databases and research studies. It is a secure web application as well as mobile application that can be used to collect, clean and manage subjects' information in accordance with various standards and applicable regulations (GCP, CFR 21 part 11, HIPAA). Furthermore, the software features amongst others a query management system and capabilities for importing and exporting data in various forms. REDCap allows for offline data collection in remote places. When connecting to the internet or cellular networks, data from the mobile device can be synchronized with the study server where the study data will be securely retained.

Paper survey forms will be used if deemed necessary (e.g. as a backup when having issues with the electronic device) or to identify households. Only data defined by the study protocol will be collected.

Questionnaires will be tested and validated before the household visits start. All study personnel will be trained on informed consent and study procedures, data collection and entry before the study start.

Edit checks and branching logic, programmed onto the electronic forms will validate at the point of data entry and support quality data. In addition, the data will be reviewed and monitored during the course of the study by various study collaborators. Data cleaning and querying of inconsistent, inaccurate and missing data will be done following a Data Validation Plan to achieve a timely database lock.

The following data will be entered in the eCRF via direct data entry:

- AE's*
- Special reporting Situations (except if reported via SAE/pregnancy report)
- PEP inclusion/exclusion criteria/eligibility
- Clinical examination
- Concomitant medication (for phase 2)
- Medical history (for phase 2)
- Visit confirmation
- Study medication administration
- TB and leprosy diagnosis, sampling, treatment and lab results
- Study withdrawal before the fourth screening round (for phase 3)Household information such as village and GPS coordinates (for phase 3)

*For phase 3 an exception is possible for spontaneous reported AE's, which might be documented on paper first.

